4.5.5.4 Cough probe

Cough probe is one of the most wide-spread functional probes performed in patients with urinary incontinence symptoms. This examination is performed according to local research center practice by functional diagnostics specialist. Probe is performed on filled urinary bladder. Female take the probe in gynecological examination chair. For probe performance patient has to cough 3 times with series of 3-4 cough impulses (with intervals between cough impulses for full inhale). When involuntary urea leaking is observed following coughing the probe is considered to be positive. Positive result designates internal sphincter failure and is typical for stress urinary incontinence diagnosis.

4.5.5.5 12-lead ECG

12-lead ECG is performed according to local practice – at screening and after the end of the study (Week 12, Visit 6). ECG copies are applied to patient's CRF. Standard ECG registration will be performed at the lying position following 5-minutes rest period. Results will be registered in the correspondent CRF pages. Primary ECG registration and/or its high-quality copy (in case of thermal paper application) should be applied to CRF. HR and PQ, QRS and QTc (Frederichi method based correction) as well as deviations of ECG outlines from normal values will be assessed.

4.5.5.6 Questionnaires, filled up by the patients

Questionnaire for hyperactive bladder symptoms assessment (OAB Awareness Tool) and health assessment questionnaire EQ-5D are to be filled by patients. EQ-5D questionnaire is to be completed during randomization (Visit 2) and after the end of therapy (Week 12, Visit 6). Questionnaire for hyperactive bladder symptoms assessment (OAB Awareness Tool) is filled out during screening for verification of inclusion criteria and during Visits 2, 3, 4, 5 and 6.

These questionnaires are required to be filled out at the beginning of the visit before discussion with the patient and performance of other visit procedures. Patient should be provided with sufficient amount of time for answers to the questions. Questionnaires should be filled out in quite place without any distracting factors. Completed questionnaire is passed from the patient to Investigator, then Investigator verifies comprehensiveness and accuracy of it filling. The investigator transfers the filled questionnaires data into the CRF.

4.6 Description of “rules for study cessation” and “inclusion criteria” for individual subjects, parts of the study and study in a whole.

Sponsor of the study, R-Pharm JSC, shall reserve the right for termination of the study anytime for reasons, including but not limited to safety problems, ethical aspects or major protocol violations (see also Section 5.3).

Moreover, R-Pharm JSC, shall reserve the right to stop the study anytime if study goals are considered to be inaccessible.

However, the Sponsor shall notify the Principal Investigator and the Head of Medical Institution concerning premature termination of the study in written form.

If the study is terminated for reasons connected to safety problems, R-Pharm JSC shall immediately notify about these circumstances all Principal Investigators and regulatory authorities and ethical boards as well.

In cases when the Principal Investigator prematurely terminates the study before its end in his/her clinical center, he or she shall immediately notify the Sponsor concerning its ceasing with explanation provided.

Moreover, the study may be terminated under requirement of regulatory authorities or ethics board for reasons, including but not limited to safety problems, in accordance to the Russian Federation and the Belarus Republic legislation.

4.7 Study products accounting procedure

The test product and the comparator product for the study will be supplied to the study organizer (CRO) by the Sponsor with correspondent acceptance and transfer certificate, analysis certificate. The responsible center employee (Investigator or authorized representative) should acquire and handle all the product supplies from the Sponsor (CRO). The product storage will be performed in locked case (applicable for storage of medicinal products) at the temperature not exceeding 25° C in a dry place protected from light, before its dispensing in specially equipped rooms with restricted access.

The Sponsor will provide research centers with the test product and comparator product in sufficient amount for performance of the study.

Control, accounting and storage of the products within research center is performed by responsible person, authorized by Principal Investigator in accordance to in-house center order and instructions from the Sponsor of the study. Study products should be stored in accordance with instructions, provided by the Sponsor, and applicable regulatory requirements.

Accounting of the test product and comparator product is performed by Investigator in Product accounting, storage and issue log. Prescription of the study product to the patients will be documented in Investigator's file (patients won't get the product personally). Investigator bears responsibility for application of study products in strict compliance with approved protocol. Any discrepancies should be provided with explanations and appropriately documented.

The Investigator will be maintaining accounting of the prescribed product for each patient, recording number and initials of patients, acquired this product, issue date, amount of issued product and date of product return by patient. Person, responsible for accounting and storage of the products and Principal Investigator draw and sign the report.

After the end of the study all unused or partially used study products should be returned to Sponsor with correspondent delivery and acceptance certificate.

4.8 Storage of randomization codes

Randomization process description is provided in Section 4.3.1.

List of randomization numbers, generated before the start of the study, will be stored in the study file in center, as well as by Sponsor or his/her Representative. Investigator bears responsibility for randomization performance (assignment of randomization number to the patient) according to this list. Randomization number, assigned to the patient, is recorded in the Screening/patients inclusion log.

Randomization numbers list will be known to investigators, Sponsor, regulatory authorities (in case of serious adverse event recognition).

4.9 List of data registered directly in CRF.

Primary data (source data) contains all information, recorded in original medical documents and approved copies, describing results of clinical observations, investigations and other activity, allowing to reconstruct clinical study course and perform its assessment. Source data are contained in primary documents (original documents or certified copies).

For each patient, participating in this study, electronic case report form (eCRF) is created, containing basic information, associated with the study.

The Sponsor will provide a separate manual (guidance) concerning eCRF handling.

This study does not provide any data that would be included into eCRF without reflection of this information in primary documents. All data, associated with this study, will be originally recorded in primary documents and then in the eCRF.

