4.3 Description of measures providing subjectivity minimization

4.3.1 Randomization

For exception of subjectivity in study product prescription randomization process is provide with use of envelopes without any additional stratification.

Overall 300 patients are planned to be randomized, that will give at least 222 patients completely finished the study (111 patients per study group).

Patients will be randomly assigned into two groups:

1. Uritos[®] (Imidafenacin, film-coated tablets; 0,1 mg, Kyorin Pharmaceutical Co. Ltd., Japan), oral, 1 tablet BID after meals (after breakfast and after supper).
2. Urotol[®] (tolterodine, film-coated tablets; 2 mg, Zentiva k.s., Czech Republic), oral, 1 tablet BID after meals (after breakfast and after supper).

Randomization is performed in 1:1 ratio. List of randomization numbers will be generated beforehand by Sponsor's data processing department or designated Contract research organization (CRO) using correspondent software package.

Sponsor will provide all research centers with the set of enumerated sealed envelopes. Each envelop contains randomization number and prescribed medicinal product. Envelopes will be sequentially numbered.

Patients, familiarized with the Patient's information list and signed Informed consent form, will be assigned numbers in order of research center visiting for screening procedures performance. During randomization visit (treatment start visit) each patient following screening and satisfying inclusion/non-inclusion criteria will be assigned unique randomization number: Investigator takes the subsequent envelop (sequentially at order of magnitude) and assigns randomization number to the patient according to the number contained in the envelope with correspondent fixation in primary documentation, CRF and Screening/patients inclusion log. Hereafter list of randomization numbers will be included into primary study file and final study report.

Randomization will be balanced around research centers so that one center would contain approximately equal number of patients, receiving test product and comparator product.

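### Sections 4.3.1 and 4.8 name different sources for the treatment assignment, and nothing says whether the centre-held list shows treatment or when sites may see it, so allocation concealment is not assured

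*Combined protocol and SAP*

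**What the plan says.** Section 4.3.1 describes an envelope procedure. The sponsor's data department or a CRO generates the list beforehand, and "Sponsor will provide all research centers with the set of enumerated sealed envelopes". On content: "Each envelop contains randomization number and prescribed medicinal product". At Visit 2 the investigator takes the next envelope in sequence and "assigns randomization number to the patient according to the number contained in the envelope". The section then adds: "Hereafter list of randomization numbers will be included into primary study file and final study report". It also says that arms will be roughly equal in size within each centre.

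Section 4.8 begins by deferring to that procedure: "Randomization process description is provided in Section 4.3.1". It then says: "List of randomization numbers, generated before the start of the study, will be stored in the study file in center", with a copy at the sponsor or its representative. Next comes: "Investigator bears responsibility for randomization performance (assignment of randomization number to the patient) according to this list". On access it says: "Randomization numbers list will be known to investigators, Sponsor, regulatory authorities (in case of serious adverse event recognition").

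Section 11.6 makes the Principal Investigator responsible for keeping the individual randomization numbers safe and returning them to the sponsor when the study ends. Section 4.3.2 makes treatment open-label. The primary ANCOVA in section 9.8 has two terms, the baseline value and the therapy group.

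**The concern.** One act, giving the next eligible patient an allocation, has two stated sources: the envelope and the list. The list exists before the first patient, sits at the enrolling centre and is said to be known to investigators. If it shows treatment, a site that follows 4.8 could know the next allocation while still deciding eligibility, and the sealed envelopes would conceal nothing.

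That decision leaves room for judgement. Section 4.5.3.2 has the criteria verified again at Visit 2 before randomization, and non-inclusion criteria 34 and 35 in section 5.2 rest on the investigator's opinion. Treatment is open-label and the primary endpoint comes from patient diaries (section 7.2), so concealment up to the moment of assignment is the main protection against selective enrolment. Baseline adjustment in the ANCOVA removes only selection that acts through baseline urination frequency. In a non-inferiority comparison, selection that favours the test product makes a false conclusion of non-inferiority more likely.

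The centre point is a separate matter. A design that balances arms within centre gains precision when centres differ, but an analysis that omits centre does not use that gain.

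**Working it through.** **Concealment: the texts side by side.** No arithmetic applies.

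| Question | Section 4.3.1 | Section 4.8 | Elsewhere |
|---|---|---|---|
| Source of assignment | Number in the next sealed envelope | The list, after a cross-reference to 4.3.1 | 4.5.3.2 refers to 4.3.1 |
| Does it show treatment? | Envelope: number and product. List: only randomization numbers mentioned | Not stated; the heading speaks of codes | Screening log records the number, not the product (4.5.1) |
| Is the list at the centre? | Filed in the primary study file, placed after the assignment step; timing unclear | Yes, and generated before the study | 11.6: numbers kept by the Principal Investigator |
| Who knows it? | Not stated | Investigators, sponsor, authorities, with a bracket on serious adverse events of unclear reach | Nothing bars site access before assignment |

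Two features of 4.8 hint at a treatment link without establishing one: the heading, and the mention of serious adverse events beside access to the list. The bracket may limit all three parties or only the authorities. The safe-keeping duty in 11.6 falls on the enrolling site's own Principal Investigator, so it does not separate the list from the enrolling team.

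**Centre in the ANCOVA: illustration.**

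Inputs: SD 2.12, margin 0.8, one-sided alpha 0.025, power 80%, 111 evaluable or 150 randomized per arm (section 9.2); about 15 centres (section 1.3). Assumed, with no source in the documents: centres explain a share ρ of residual variance, from 5% to 15%.

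1. Plan's figure: 2 × 2.12² × (0.84 + 1.96)² / 0.8² = 110.1, rounded up to 111 per arm. It reproduces.
2. Standard error: 2.12 × √(2/111) = 0.2846; with 150 per arm, 0.2448.
3. Half-width without centre: 1.96 × 0.2846 = 0.558 episodes per day. With centre it is multiplied by √(1 − ρ): 0.544 (ρ = 0.05) and 0.514 (ρ = 0.15).
4. Excess width: 1/√(1 − ρ) − 1 = 2.6% and 8.5%.
5. Actual one-sided error without centre: Φ(−1.96/√(1 − ρ)) = 0.0222 and 0.0168, against 0.025.
6. Power at a true difference of zero. Without centre: Φ((0.8 − 1.96·SE)/(SE·√(1 − ρ))). With centre: Φ(0.8/(SE·√(1 − ρ)) − 1.96).

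| Per arm | ρ | Without centre | With centre |
|---|---|---|---|
| 111 | 0.05 | 0.809 | 0.822 |
| 111 | 0.15 | 0.822 | 0.862 |
| 150 | 0.05 | 0.910 | 0.918 |
| 150 | 0.15 | 0.922 | 0.943 |

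7. Cost: residual degrees of freedom fall from 222 − 3 = 219 to 219 − 14 = 205. The t quantile rises by a factor of 1.0004, about 0.04% of width.

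Steps 3 to 6 use the one-sided 97.5% level of section 9.3. Section 9.8 states 95%; at that level the error in step 5 would be 0.046 and 0.037 against 0.05.

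**The case against.** The strongest reply is that the two sections can be read together. Section 4.8 sends the process to 4.3.1. What it says is assigned from the list is the randomization number, not the product, and only the envelope is said to contain the product. Envelopes prepared from a list of numbers would fit both sections, and the filing sentence in 4.3.1 can be read as filing after assignment. All of this stands as a possible reading. It does not settle the matter, because no section says what the list contains or keeps it from the enrolling team.

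The room for selection is also limited. Section 4.2 allows at most 350 screened for 300 randomized, so at most 350 − 300 = 50 patients are not randomized if the target is met. Screening lasts no more than 14 days, most criteria are objective, numbers are never reused, and the log of dates and numbers would let an audit find use out of order. These features restrict selective enrolment but do not exclude it.

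A reader might also infer that 4.3.1 contradicts itself by ruling out additional stratification while balancing by centre. The documents do not support that: the phrase can mean none beyond centre. Nor do they support a complaint that blocking is exposed, since the protocol discloses no block size.

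On centre, the plan as written is conservative and its power stays above 80%. The calculation also applies an assumed centre share to 2.12, which is an unadjusted SD of change and not the ANCOVA residual. Both objections stand, so the figures are illustrative only.

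**Conclusion.** The point holds as an unresolved conflict. Section 4.3.1 assigns from the envelope and section 4.8 from a centre-held list known to investigators. The content of that list and the timing of access are not stated, so concealment is not assured.

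A reader might go further and infer that concealment is broken, or that the type I error is inflated by some amount. The documents support neither. Harm arises only if the list shows treatment and is seen before assignment, and the documents give nothing from which to derive a size of bias.

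The centre point concerns precision only. Omitting centre causes no bias and misses no stated design target. Under the assumed 5% to 15% share, the interval is about 2.6% to 8.5% wider than needed, and 1.4 to 4.0 percentage points of power are forgone at 111 per arm (0.8 to 2.1 at 150). It adds no weight to the concealment point.

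**What to change.** **1. Concealment.**
- In 4.8, delete the last four words of "Investigator bears responsibility for randomization performance (assignment of randomization number to the patient) according to this list", and remove investigators from the sentence on who knows the list. State that assignment follows only the sealed-envelope procedure in 4.3.1.
- Amend the storage sentence in 4.8, the filing sentence in 4.3.1 and the custody sentence in 11.6 so that any list linking numbers to treatment is held only by the sponsor or CRO until enrolment ends. If the centre list holds numbers only, say so.

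This is a wording change that needs no new staff or systems, since the envelopes are already supplied. Section 11.7 exempts logistic and administrative amendments from ethics approval, and section 12.2 allows notification alone for slight inaccuracies. The sponsor must judge which route applies.

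**2. Precision (separate).** Add centre as a factor in the primary ANCOVA in 9.8, with a pre-specified rule for pooling small centres. This costs about 14 degrees of freedom and, because it changes the analysis plan, a protocol amendment under section 9.6.

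At most, 4.3.1 could also say that there is no stratification other than by centre. No statement on blocking details is needed.

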5 PATIENTS SELECTION AND EXCLUSION

5.1 Inclusion criteria

For participation in the study patient should satisfy all the listed criteria:

1. Informed consent signed and dated;
2. Male and female patients with age range between 18 and 65 years (age at the moment of signing informed consent form).
3. Documented overactive bladder (OAB) diagnosis. OAB diagnosis is established on characteristic symptoms of the patient:
 - a. urinary incontinence – 5 and more episodes per week;
 - b. frequent urination – 8 and more times per day;
 - c. Micturition urgency – 1 and more episodes per day.
4. OAB symptoms duration 3 months and more (assessment is based on patient history and medical documents).
5. Overactive bladder Awareness Tool Questionnaire (OAB Awareness Tool) score 8 and more at the screening visit and randomization visit.
6. Negative dipstick pregnancy test at screening and at randomization visit before administration of the first dose of the study product in female patients of childbearing potential.
7. Female patients of childbearing potential and male patients and their female partners should use at least two birth control methods, one of those is barrier, during the whole study period and at least 35 days following administration of the last dose of the study product. Permissible birth control methods:
 - oral, transdermal, implantational and injectional hormonal therapy;
 - efficient intrauterine devices;
 - double barrier contraceptive methods.
8. Willingness and ability to follow study visits schedule, treatment plan, laboratory tests and other study procedures.

5.2 Non-inclusion criteria

For participation in the study patient should be free from all the following criteria:

1. Patient history of hypersensitivity or suspected hypersensitivity to tolterodine or imidafenacin.
2. Structural pathology of urinary bladder, including urinary bladder cancer, urinary bladder stones and interstitial cystitis.
3. Residual urea volume 100 mL and more at US-examination of urinary bladder.
4. Documented diagnosis of stress urinary incontinence.
5. Surgical interventions on urinary bladder and urethra during the previous 6 months or indications for surgical treatment due to OAB.
6. Exacerbation of gynecological diseases including endometriosis, uterine leiomyoma exceeding 3 cm in diameter.
7. Prostate carcinoma.
8. Prostate diseases with clinically significant urodynamics abnormality (benign prostatic

hyperplasia, acute and chronic prostatitis, prostatic calculus).

9. Renal and urine excretory ways inflammatory disorders (pyelonephritis, bacterial cystitis, urethritis).
10. For male PSA level above 4 ng per mL.
11. Severe liver function abnormality (ALT and/or AST level 3 and more times exceeding upper limit of normal and/or total bilirubin level 1.5 times exceeding upper limit of normal).
12. Moderate or severe renal function abnormality based on medical information and/or glomerular filtration rate < 50 ml/min by Cockcroft-Gault formula and/or blood creatinine level > 133 µmol during screening.
13. Positive test result for hepatitis B, hepatitis C and HIV.
14. Patients suffering from neoplastic condition without remission, at least, within 5 years from the start of administration of the study product.
15. Vascular dementia, Alzheimer disease associated dementia, dementia associated with other diseases including organic amnesic syndrome.
16. Parkinson's disease and secondary parkinsonism.
17. Nonspecific ulcerative colitis including severe stage of ulcerative colitis.
18. Thyroid gland pathology with hyperthyroidism signs.
19. Chronic heart insufficiency Stage III-IV by NYHA.
20. Hypotension: systolic blood pressure < 90 mm Hg and/or diastolic blood pressure < 60 mm Hg.
21. Non-controlled medically induced hypertension.
22. Hemodynamically and/or clinically significant heart arrhythmias.
23. Prolongation of QTc interval up to 450 ms and more in males and 470 ms and more in females.
24. Closed-angle glaucoma.
25. Myasthenia gravis.
26. Megacolon, paralytic ileus, pyloric part of the stomach/duodenal occlusion and any other conditions associated with clinically significant gastric/intestinal passage obstruction or depressed motility.
27. Necessity of intake and/or intake of prohibited products, declared in the Section "Acceptable and prohibited recent and concomitant therapy" within 7 days before the start of therapy.
28. Drug abuse, chronic alcoholism, any psychotic disorders.
29. Participation in other studies within 3 months from the start of the current study and/or during this study.
30. Pregnancy and/or breastfeeding.
31. Female patients of childbearing potential, having unprotected sexual contact with male person, non-sterilized by vasectomy during, at least, 6 months, within 14 days before administration of the study product.
32. Inability to follow protocol procedures.
33. Any other acute or exacerbation and/or decompensation of chronic diseases at the

moment of inclusion into the study.

34. Patient's behavior, any safety reasons, clinical and administrative reasons, which, according to Investigator's opinion, may potentially influence study product safety/efficiency assessment.

35. Other medical and psychiatric conditions or deviations of laboratory parameter which may increase patient risk associated with participation in the study or administration of the study product, or which can influence interpretation of the study results and, according to Investigator's opinion, make person not satisfying conditions for participation in this study.

36. Patients being employees of the research center or patients being employees of Sponsor/CRO, directly involved into performance of this clinical study.

